## **10. STATISTICAL CONSIDERATIONS**

### **10.1 Study Endpoints, Analysis Sets, and Covariates**

#### **10.1.1 Study Endpoints**

##### **10.1.1.1 Primary Endpoint**

- Subject grade, incidence and severity of DLTs and adverse events

Approved

#### 10.1.1.2 Secondary Endpoints

- Blinatumomab PK parameters under cIV and SC administrations
- MTD
- Incidence of anti-blinatumomab antibodies
- ORR (complete response [CR] + partial response [PR]) as determined by best overall response using Cheson criteria ([Appendix A](#))

#### 10.1.1.3 Exploratory Endpoints

- PD parameters of B- and T-lymphocytes and cytokines following administration of SC blinatumomab
- ORR (CR + PR) as determined by best overall response using Lugano criteria ([Appendix B](#))

#### 10.1.2 Analysis Sets

The statistical analysis will be based on the following study populations. Subjects will be summarized separately by the planned dose cohorts.

The analysis of all endpoints, unless noted otherwise, will be conducted on the Full Analysis Set.

The analysis of DLTs will be restricted to DLT-evaluable subjects.

##### 10.1.2.1 Full Analysis Set

All subjects who receive blinatumomab are included in the full analysis set. This definition is in line with the intent-to-treat principle in single-arm open-label studies.

##### 10.1.2.2 Safety Analysis Set

For each part of the study, the safety analysis set will be the same as the full analysis set.

##### 10.1.2.3 DLT Analysis Set

All subjects who are DLT-evaluable are included in this analysis set as defined in [Section 6.2.1.2.2](#).

##### 10.1.2.4 Pharmacokinetic Analyses Set

All subjects who received any blinatumomab and had at least one PK sample collected will be included in the PK analysis set. These subjects will be evaluated for PK unless significant protocol deviations affect the data analysis or if key dosing, dosing interruption, or sampling information is missing.

Approved

#### 10.1.2.5 Pharmacodynamic Analyses Set

All subjects who had cytokine and/or lymphocyte subset samples collected at any time during the study will be included in the PD analysis set.

#### 10.1.3 Covariates and Subgroups

The relationship of the certain baseline covariates to endpoints will be explored if appropriate. Biomarker data may be incorporated in additional exploratory subgroup or multivariate analyses. The analyses of biomarkers may be performed after collection of all samples during the conduct of the study and therefore may be reported after the final analysis.

#### 10.2 Sample Size Considerations

Approximately **54** evaluable subjects will be enrolled in the study.

Six evaluable subjects will be enrolled at each SC dose level in Cycle 1/Period 1. Subjects may be replaced (replacement rules outlined in [Section 3.4](#)). This sample size is based on practical considerations and is consistent with conventional phase 1 oncology studies. If the true DLT rate is 10%, there is an 89% probability of observing  $\leq 1$  DLT and 11% probability of observing 2 or more DLT in 6 subjects. If the true DLT rate is 30%, the probability of observing  $\leq 1$  DLT decreases to 42% and probability of observing 2 or more DLT increases to 58%.

Up to 15 evaluable subjects will be enrolled into Cycle 1/Period 2 with the planned target treatment dose being the highest tolerable dose regimen or highest tested dose regimen based on DLRT's recommendations. Continuous toxicity monitoring for early termination of the trial in Cycle 1/Period 2 will be performed. Termination of the study in Cycle 1/Period 2 will occur if the posterior probability that the DLT rate greater than 25%, given the cumulative data thus far is at least 80%. Starting with the fifth subject treated in Cycle 1/Period 2, stopping may occur any time. The stopping boundaries assume a prior beta distribution of (0.50, 1.50) and a batch size of 1 (starting with the fifth subject treated) are presented in [Table 10](#) and the operating characteristics are given in [Table 10](#). The operating characteristics in [Table 10](#) provide the probability of stopping the trial early for given hypothetical true DLT rates whereas the stopping criteria in [Table 10](#) are based on situations where the empirical evidence would result in a posterior probability  $\geq 80\%$  that the true DLT rate is  $\geq 25\%$  ([Thall et al, 1995](#)).

Approved

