## 5. SUBJECT ENROLLMENT

Before subjects begin participation in any study-specific activities/procedures, Amgen requires a copy of the site's written institutional review board/independent ethics

committee (IRB/IEC) approval of the protocol, informed consent form, and all other subject information and/or recruitment material, if applicable (see [Section 11.2](#)).

Subject must personally sign and date the IRB/IEC and Amgen approved informed consent form before the commencement of study-specific procedures. Upon completion of the screening period the subject is evaluated by the investigator and providing the subject continues to meet the inclusion/exclusion criteria, the subject is subsequently eligible to be enrolled in the study and assigned to a treatment regimen (dose cohort).

A subject is considered enrolled when the investigator decides that the subject has met all eligibility criteria. The investigator is to document this decision and date, in the subject's medical record and in/on the enrollment case report form (CRF).

Each subject who enters into the screening period for the study receives a unique subject identification number before any study-related activities/procedures are performed. The subject identification number will be assigned manually. This number will be used to identify the subject throughout the clinical study and must be used on all study documentation related to that subject. A subject may be rescreened up to 3 additional times during the study at the discretion of the investigator.

The subject identification number must remain constant throughout the entire clinical study; it must not be changed after initial assignment, including if a subject is rescreened.

There will be a 96-hour interval between the start of treatment of each subject entered on study. See [Section 6.2.1.4.2](#) for interruption of blinatumomab treatment/dose modification due to adverse events.

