#### 6.2.1.2.2 Dose Limiting Toxicity Rules

##### Cycle 1/Period 1

The DLT evaluation period includes the entire **week 4 (7 days) which is the week that blinatumomab is administered** SC during Cycle 1/Period 1 of the study. To be evaluable for a DLT, subjects must have experienced a DLT within the DLT evaluation period. In addition, if the investigator and/or sponsor removes the subject from the study due to a treatment-related toxicity during the DLT evaluation period, regardless of the grade of toxicity, this will be considered a DLT. If a subject does not experience a DLT during the DLT evaluation period and does not receive **all doses (q48h, q72h, q96h, or q7d dosing)**, at least 4 of the 5 doses (q24h dosing), or at least 8 of 9 doses (q12h dosing) of **SC** blinatumomab during Cycle 1/Period 1 of the study, the subject will not be considered DLT-evaluable and will be replaced as described in [Section 3.4.1](#).

If  $\leq 1$  of the 6 evaluable subjects in a dose SC cohort experience a DLT during the SC administration, then the dose will be determined to be tolerable and the next dose-cohort level will be initiated in a new dose-cohort of subjects after review by the DLRT.

If  $\geq 2$  subjects of the 6 evaluable subjects in a SC dose cohort experience a DLT during SC administration then dosing will stop for individual subjects who experience a DLT, a DLRT meeting will be conducted, and further steps will be determined.

Additionally, the DLRT will meet:

- once dose-cohort 1 has completed subcutaneous dosing
- once dose-cohorts 2 and 3 have completed subcutaneous dosing
- once any additional cohorts complete dosing if additional dose-cohorts are tested to determine the MTD in Cycle 1/Period 1

## Cycle 1/Period 2

For subjects who receive optional Cycle 2 after Cycle 1/Period 2 (SC dosing period), the DLT evaluation period includes the entire duration of SC administration **in Cycle 1** and 16 days following the last SC dose (56 days in total) or until the start of optional Cycle 2, whichever is longer, up to 30 days after the last SC dose **of Cycle 1**.

For subjects who do not receive optional Cycle 2, the DLT evaluation period includes the entire duration of SC administration and 30 days following the last SC dose (70 days in total).

Continuous monitoring for early termination of the trial will be performed (refer to [Section 10.2](#)).

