If the outcome of the underlying disease is worse than that which would normally be expected for the subject, or if the investigator believes there is a causal relationship between the IP(s)/study treatment protocol required therapies and disease worsening, this must be reported as an adverse event or a serious adverse event. [Table 3](#) outlines the expected Disease-Related Events by System Organ Class (SOC).

Table 3. Disease-related Adverse Events by System Organ Class

System Organ Class (SOC)	Preferred Terms
Blood and lymphatic system disorders	Lymphadenopathy
General disorders and administration site conditions	Disease progression Fatigue
Investigations	Weight decreased
Skin and subcutaneous tissue disorder	Night sweats

Disease Related Events that would qualify as an Adverse Event or Serious Adverse Event:

- An event based on the underlying disease that is worse than expected as assessed by the investigator for the subject's condition or if the investigator believes there is a causal relationship between the investigational product(s)/study treatment/protocol-required therapies and disease worsening, this must be reported as an Adverse Event or Serious Adverse Event.

DLT Evaluable

Period 1:

To be evaluable for DLT, subjects must meet one of the following criteria:

- Cohort I and II: received treatment for or at least 8 of the 9 doses or experienced a DLT at any time while receiving blinatumomab.
- Cohort III: treated at least 4 of the 5 doses or experienced a DLT at any time while receiving the target dose of blinatumomab.

If a subject does not experience a DLT during the DLT evaluation period and does not receive all doses (q48h, q72h, q96h, or q7d dosing), at least 4 of the 5 doses (q24h dosing) or at least 8 of the 9 doses (q12h dosing) of subcutaneous Blinatumomab and taken off study for reasons other than toxicity the subject will not be considered DLT-evaluable and will be replaced as described in Protocol Section 3.4.1.

Period 2:

To be evaluable for DLT, subjects must meet one of the following criteria:

- If only cycle 1 is given : experienced a DLT during the entire duration of the SC administrations and 30 days after the last SC dose or treated with blinatumomab targeted dose for 5 days.

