- If cycle 2 is given: experienced a DLT during the entire duration of the SC administrations and 16 days following the last SC dose or until the start of cycle 2 (whichever is longer), up to 30 days after the last SC dose or treated with blinatumomab at 112 µg/day cIV for 42 days.

Dose Limiting Toxicity (DLT)

The occurrence of any of the toxicities mentioned in the section 6.2.1.2.3 of the protocol will be considered a DLT, if judged by the investigator to be related to administration of blinatumomab.

ECOG Performance Status Assessment

ECOG performance status assessment will be performed using the ECOG score. For more details please refer appendix C in Protocol.

End of Study for Individual Subject

End of IP Administration for subjects who had blinatumomab is defined as the date the decision was made to end IP as recorded on the End of IP CRF page.

End of Treatment

Defined as the last assessment for the protocol-specified treatment phase of the study for an individual subject.

End of Follow-up

Defined as the date that the last subject completes the last protocol-specified assessment in the study.

Enrollment Date

Enrollment Date is defined as the date of enrollment collected on the CRF.

Subject Level End of Study (EOS) Date

End of study for each subject is defined as the date the subject last completed a protocol-specified procedure. The date will be recorded on the End of Study CRF page.

Investigational Product

The term 'investigational product' is used in reference to blinatumomab.

Last Dose Date of Investigational Product

This is the stop date of the last dose of blinatumomab administration reported on the Investigational Product Administration CRF.

Maximum Tolerated Dose (MTD)

MTD will be defined as the highest dose level at which ≤ 1 of 6 subjects experience a DLT. If no subject experiences a DLT, the MTD will be defined as the maximal dose tested.

Optional Cycle 2

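### The Period 2 operating characteristics hold only if each DLT outcome is known before the next enrolment decision, and the plan does not say how a subject with an open DLT window counts

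*Protocol*

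**What the plan says.** Protocol 10.2, repeated in SAP 3.1.3, stops Cycle 1/Period 2 when the posterior probability of a DLT rate above 25% reaches 80%. The prior is Beta(0.5, 1.5) with a look after every subject: "Starting with the fifth subject treated in Cycle 1/Period 2, stopping may occur any time". Table 10 (SAP Table 1) sets boundaries against a running count of subjects without saying which subjects are in it. Table 11 (SAP Table 2) gives stopping probabilities and average sample sizes.

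Other text points to a different denominator from subjects treated. Protocol 10.2 also says "Up to 15 evaluable subjects will be enrolled into Cycle 1/Period 2". Protocol 10.1.2 says "The analysis of DLTs will be restricted to DLT-evaluable subjects". Protocol 10.1.2.3 says "All subjects who are DLT-evaluable are included in this analysis set as defined in" Section 6.2.1.2.2.

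On timing, Protocol 6.2.1.2.2 states, for a subject treated in Cycle 1 only, that "the DLT evaluation period includes the entire duration of SC administration and 30 days following the last SC dose (70 days in total)". With Cycle 2 the window is 56 days, or longer if Cycle 2 starts later, up to 30 days after the last SC dose. The only spacing given is in Protocol 5: "There will be a 96-hour interval between the start of treatment of each subject entered on study".

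For a DLT-free Period 2 subject, SAP Section 6 requires "treated with blinatumomab targeted dose for 5 days" if only Cycle 1 is given, and 112 µg/day "cIV for 42 days" if Cycle 2 is given.

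Protocol 3.3 plans about 54 enrolled for about 30 plus up to 15 evaluable, with about 20% expected to discontinue early. Protocol 10.2 calls the same 54 evaluable. The SAP 3.2 example ties stopping chances of 17% and 45% to Period 1 and to sizes of 14 and 12.

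**The concern.** Period 2 gives SC dosing without a cIV run-in, and the posterior rule is its only quantified cohort-level stopping rule. Table 11 is where a reader judges how often the rule would halt an over-toxic regimen and how many subjects would start treatment first. A table built on immediate outcomes fits poorly with a window of eight to ten weeks and starts that may be four days apart.

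The missing counting rule has a practical consequence. Two teams holding the same data could reach opposite decisions, depending on whether a DLT-free subject with an open window is already in the denominator. The rule is worded as mandatory termination, so its denominator should be fixed in advance.

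**Working it through.** **1. Reproduce the stated tables.** After s DLTs in n subjects the posterior is Beta(0.5+s, 1.5+n−s); stop if P(rate > 0.25) ≥ 0.80. At n = 6, s = 2 gives 0.61 and s = 3 gives 0.86, so the boundary is 3. At n = 7, s = 3 gives 0.7996, just short, so it is 4. For n = 5 to 14 the boundaries are 3, 3, 4, 4, 4, 4, 5, 5, 5, 6, as in Table 10. An exact binomial recursion with looks at n = 5 to 14, maximum 15, and every outcome known at once gives:

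| True rate | Stop, recomputed | Stop, stated | Mean N, recomputed | Mean N, stated |
|---|---|---|---|---|
| 20% | 17.4% | 17% | 13.69 | 13.7 |
| 25% | 30.3% | 30% | 12.73 | 12.7 |
| 30% | 44.9% | 45% | 11.60 | 11.6 |
| 40% | 72.4% | 72% | 9.25 | 9.3 |
| 50% | 90.2% | 90% | 7.32 | 7.3 |
| 60% | 97.8% | 98% | 6.06 | 6.1 |

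Both tables are right under that assumption.

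**2. Timing.** At 96-hour spacing the 15th subject can start 14 × 4 = 56 days after the first. No 70-day window has closed by then, and the first 56-day window is only just ending.

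**3. Effect of the counting rule.** Assumptions, not document figures: fixed spacing, 15 planned starts, DLT onset uniform over 21 or 42 days from first dose, a decision before each start from the sixth. A DLT counts when it occurs. A DLT-free subject enters the denominator at first dose, at day 17 (target dose from day 12 plus the SAP's 5 days) or at day 70 (window close). With fewer than five counted, three DLTs stop (Table 10 note). Simulated probability of stopping enrolment at 4-day spacing, 21-day / 42-day onset (60,000 trials per setting, good to about one point):

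| True rate | Stated | First dose | Day 17 | Window close |
|---|---|---|---|---|
| 20% | 17% | 9 / 3% | 20 / 10% | 43 / 28% |
| 30% | 45% | 28 / 11% | 47 / 29% | 74 / 55% |
| 50% | 90% | 77 / 46% | 90 / 73% | 98 / 90% |

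At a 50% rate with day-17 counting, mean N at 4/7/14/28-day spacing is 8.6/7.8/7.5/7.3 (21-day onset) and 11.3/9.4/8.1/7.6 (42-day onset), against 7.3 stated.

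Sensitivities:
- At 28-day spacing and a 50% rate, every counting rule gives 89 to 92% with these two onset ranges. The largest gap found at that spacing comes from onset over days 12 to 70 with first-dose counting: 24/37/65% against 30/45/72% at true rates of 25/30/40%, at most about 8 points.
- The same late onset at 4-day spacing with first-dose counting gives about 0/1/6% at true rates of 25/40/60%, against 30/72/98%. The 21- and 42-day results are therefore not outer bounds.
- At a 50% rate and 4-day spacing, entry at day 16 instead of 17 gives 88% (21-day onset) and 66% (42-day onset).
- If crossings after the 15th start also count (50% rate, 4-day spacing, 42-day onset), day-17 counting rises from 73% to 84%. First-dose counting stays at 46%, because Table 10 has no boundary at 15.

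**4. Period 2 evaluability, side by side.**
- Protocol 6.2.1.2.2: a window, but no minimum-exposure criterion.
- Protocol 3.4.2: replacement turns on 85% of the first 8 doses (0.85 × 8 = 6.8). By Table 6 the eighth dose falls on day 16 (q48h), 18 (q72h), 20 (q96h) or 26 (q7d).
- SAP 6, Cycle 1 only: 5 days at the target dose.
- SAP 6, Cycle 2 given: 42 days at 112 µg/day cIV. The SAP's own cIV Cycle 2 has that level on days 15 to 42, which is 42 − 15 + 1 = 28 days, and an SC Cycle 2 has none. A DLT-free subject who takes Cycle 2 cannot meet this criterion on the planned schedule.

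**5. SAP 3.2 example.** SAP Table 2 pairs 17% with 13.7 and 45% with 11.6. The 14 and 12 are those averages rounded, and both belong to the Period 2 rule with a maximum of 15. Were 12 a fixed maximum, stopping at a 30% rate would be 0.395 to 0.415, not 0.45.

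**6. Enrolment.** 30 + 15 = 45, and 45 × 1.2 = 54. The loss that 54 absorbs is 1 − 45/54 = 16.7%. At 20% loss, 54 × 0.8 = 43.2.

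**The case against.** Boundary tables with immediate outcomes are a usual way to present such a rule. The 96 hours is a safety gap, not an accrual forecast, and 15 subjects starting exactly four days apart is the fastest permitted case. The Amendment 6 rationale reports only 12 subjects treated SC by early 2019, which suggests slower accrual, though the first-subject date is not given. Early onset is what Protocol 2.4 (cytokine release after initiation) and 6.2.1.1.4 (close monitoring in the first 72 hours at each dose) suggest. With early onset and day-17 counting, the stated stopping probabilities hold to within about 3 points and only mean N rises. The wording about the fifth subject treated leans towards counting treated subjects, and the DLRT can delay or end dosing at its discretion (Protocol 6.2.1.2.1, 10.3.1).

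Most of this stands, and it limits the size of the point. It does not supply the missing rule: the treated wording conflicts with the DLT-evaluable wording, neither deals with open windows, and discretionary review does not define the denominator of a mandatory rule.

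A reader might infer that Tables 10 and 11 are miscalculated; they are not. A reader might infer that the rule will miss toxic regimens; window-close counting stops as often as stated or more often at 4-day spacing with 21- or 42-day onset. A reader might infer that the trial is under-enrolled, or will yield only 43 evaluable subjects; Protocol 3.3 uses approximate targets and says lost subjects are replaced, so that does not follow. SAP 3.2 states no loss rate and has no such error.

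**Conclusion.** The concern holds as a gap in specification, not as a calculation error. Table 11 rests on an unstated assumption that the design does not secure, and the counting rule is missing. At 4-day starts with onset over 21 or 42 days, the choice of rule moves stopping between 46% and 98% at a 50% true rate, and between 3% and 43% at 20%. At monthly starts the gap is at most about 8 points for the three onset ranges tested. Accrual and onset are assumptions throughout, and the large figures belong to the fastest permitted accrual.

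Three further defects do not depend on those assumptions: the Period 2 evaluability texts conflict, one SAP criterion cannot be met on the SAP's own schedule, and the SAP 3.2 example is wrong about both period and sample size. The word evaluable attached to 54 in Protocol 10.2 contradicts Protocol 3.3 and SAP 3.2. The 16.7% against 20% is minor. These should be corrected before the rule is applied.

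**What to change.** 1. State in Table 10 and SAP Table 1 how a subject with an open DLT window counts.
2. Label Table 11 and SAP Table 2: *Assumes each subject's DLT outcome is known before the next enrolment decision.* Add a re-run for the chosen counting rule under the actual window and a stated range of accrual and onset.
3. Reconcile Protocol 3.4.2, Protocol 6.2.1.2.2 and the two Period 2 criteria in SAP 6 with each other and with the SAP's Optional Cycle 2 schedule.
4. Delete the SAP 3.2 example, or tie 17% and 45% to the Cycle 1/Period 2 rule with a maximum of 15 and average sample sizes of 13.7 and 11.6.
5. In Protocol 10.2 drop the word evaluable from the 54. In Protocol 3.3 restate the allowance as about 17% of enrolled subjects, that is 9 replacements for 45 evaluable. SAP 3.2 needs no change on yield.

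The cost is wording in both documents and one re-run table, with no change to planned enrolment. The counting rule is the sponsor's choice and carries a trade-off: one that stops a toxic regimen more often also stops an acceptable one more often. At a 20% true rate and 4-day starts, stopping is 3 to 9% counted at first dose, 10 to 20% at day 17 and 28 to 43% at window close.

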### 3.3 Number of Subjects

Participants in this clinical investigation shall be referred to as “subjects”.

Approximately **54** subjects will **be enrolled** in this study **in order to ensure approximately 30 evaluable subjects in Period 1 and up to 15 evaluable subjects in Period 2 are treated with blinatumomab. It is expected that approximately 20% of subjects will discontinue the study prematurely (ie, due to adverse event, subject request, requirement for alternative therapy) during the cIV run-in period**

(Cycle 1/Period 1) or prior to receiving sufficient SC dosing (Cycle 1/Period 2 weeks 1 to 3) and will need to be replaced per [Section 3.4](#). Refer to [Section 10.2](#) for sample size considerations.

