**Table 10. Cycle 1/Period 2 Stopping Boundaries**

Cumulative Number of Subjects	Stop Study if This Many Subjects Have a Dose-limiting Toxicity
5 - 6	≥ 3
7 - 10	≥ 4
11 - 13	≥ 5
14	≥ 6
15	Study Period 2 is complete at 15

**Note:** Study may stop with fewer than 5 subjects if 3 or more subjects with DLTs have been observed

**Abbreviation:** DLT = dose limiting toxicities

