3.1.3 Safety Monitoring

Safety monitoring will be implemented using continuous toxicity monitoring for early termination of the trial in Cycle 1/Period 2. Termination of study Cycle 1/Period 2 will occur if the posterior probability that the DLT rate is greater than 25%, given the cumulative data thus far, is at least 80%. Starting with the fifth subject treated in Cycle 1/Period 2, stopping may occur at any time.

The stopping boundaries assume a prior beta distribution of (0.50, 1.50) and a batch size of 1 (starting with the fifth subject treated) are presented in [Table 1](#) and the operating characteristics are given in [Table 2](#). The operating characteristics in [Table 2](#) provide the probability of stopping the trial early for given hypothetical true DLT (please see [section 6](#) for more details) rates whereas the stopping criteria in [Table 1](#) are based on situations where the empirical evidence would result in a posterior probability $\geq 80\%$ that the true DLT rate is $\geq 25\%$ ([Thall et al, 1995](#)).

Table 1. Cycle 1/Period 2 Stopping Boundaries

Cumulative Number of Subjects	Stop Study if This Many Subjects Have a Dose-limiting Toxicity
5 - 6	≥ 3
7 - 10	≥ 4
11 - 13	≥ 5
14	≥ 6
15	Study Period 2 is complete at 15

[figure not shown]
Note: Study may stop with fewer than 5 subjects if 3 or more subjects with DLTs have been observed

Table 2. Operating Characteristics

True Rate of Dose-Limiting Toxicities	Probability of Stopping Early	Average Sample Size
20%	17%	13.7
25%	30%	12.7
30%	45%	11.6
40%	72%	9.3
50%	90%	7.3
60%	98%	6.1

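### The Period 2 toxicity stopping rule does not say whether it counts treated or DLT-evaluable subjects; applied literally to treated subjects, it can stop less often than Table 11 states

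*Protocol*

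**What the plan says.** **The rule.** Protocol 10.2 stops Period 2 when the posterior probability of a DLT rate above 25% is at least 80%. It uses a Beta(0.50, 1.50) prior and looks after every subject from the fifth onwards. The only word tied to the count is 'treated': "Starting with the fifth subject treated in Cycle 1/Period 2, stopping may occur any time". SAP 3.1.3 agrees: "Starting with the fifth subject treated in Cycle 1/Period 2, stopping may occur at any time". Protocol Table 10 and SAP Table 1 head the count "Cumulative Number of Subjects" and end at 15.

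**The cohort and the analysis.** The same protocol section says "Up to 15 evaluable subjects will be enrolled into Cycle 1/Period 2". Protocol 10.1.2 says "The analysis of DLTs will be restricted to DLT-evaluable subjects".

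**Replacement.** Protocol 3.3 states: "It is expected that approximately 20% of subjects will discontinue the study prematurely". It applies this to Period 2 subjects who leave in weeks 1 to 3 before enough SC dosing, and says they will need to be replaced. Protocol 3.4.2 allows replacement of a subject who receives less than 85% of the first 8 planned doses, but never of one removed for a DLT.

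**Not stated.** Neither document says whether a treated, replaced subject without a DLT stays in the denominator of the stopping rule.

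**The concern.** Subjects removed for a DLT are never replaced, so a replaced Period 2 subject is DLT-free. Counting such a subject adds to the denominator and nothing to the numerator, which can only move the rule away from stopping. Table 11 has no allowance for this.

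This is the only numerical stopping rule for the SC-only regimen, which has no cIV run-in. As written, two statisticians with the same data could reach opposite decisions: one following the word 'treated', the other following the evaluable cohort and the DLT analysis set. A safety boundary needs a single denominator, fixed before data accrue.

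**Working it through.** **Inputs.** Prior, threshold and look schedule come from Protocol 10.2, boundaries from Table 10, operating characteristics from Table 11. Protocol 3.3 and SAP 3.2 plan 54 enrolled to obtain 30 + 15 = 45 evaluable. That implies a non-evaluable share of (54 − 45)/54 = 16.7%. The 20% expectation in Protocol 3.3 is the other documented figure. Shares of 5% and 10% are my assumptions, to show the range. Treating early discontinuation as non-evaluable and DLT-free is also an assumption.

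**Step 1: reproduce Table 10.** After x DLTs in n subjects the posterior is Beta(0.5 + x, 1.5 + n − x). The smallest x with Pr(rate > 0.25) ≥ 0.80 is 3 at n = 5–6, 4 at 7–10, 5 at 11–13 and 6 at 14. This is Table 10.

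**Step 2: reproduce Table 11.** Exact binomial recursion: a look after each subject from 5 to 14, maximum 15, every subject able to have a DLT with probability p.

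| True DLT rate | Table 11: P(stop), average n | Recomputed |
|---|---|---|
| 20% | 17%, 13.7 | 17.4%, 13.7 |
| 25% | 30%, 12.7 | 30.3%, 12.7 |
| 30% | 45%, 11.6 | 44.9%, 11.6 |
| 40% | 72%, 9.3 | 72.4%, 9.3 |
| 50% | 90%, 7.3 | 90.2%, 7.3 |
| 60% | 98%, 6.1 | 97.8%, 6.1 |

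Table 11 is therefore correct if every counted subject is evaluable.

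**Step 3: count treated subjects instead.** Each treated subject is non-evaluable without a DLT with probability d, evaluable without a DLT with probability (1 − d)(1 − p), or has a DLT with probability (1 − d)p. All enter n. Treatment continues, with replacement, until 15 are evaluable or the rule stops. Table 10 ends at 14, so the same posterior criterion is extended: 6 DLTs at 15–16 treated, 7 at 17–20, 8 at 21–23, and so on.

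| Non-evaluable share d | P(stop), true rate 30% | P(stop), true rate 40% | P(stop), true rate 50% |
|---|---|---|---|
| 0 (Table 11) | 45% | 72% | 90% |
| 5% | 41% | 69% | 88% |
| 10% | 38% | 65% | 86% |
| 16.7% (9/54) | 32% | 59% | 82% |
| 20% | 30% | 56% | 79% |

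**Step 4: a single subject can change the decision.** Three DLTs in 6 evaluable subjects give Beta(3.5, 4.5) and a posterior probability of 0.862: stop. With one earlier non-evaluable subject counted, the same data are 3 of 7, Beta(3.5, 5.5), 0.7996: continue.

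Because looks follow every subject, this needs one non-evaluable subject and two DLTs among the first six treated, with the third DLT in the seventh. At d = 1/6 and p = 0.40, (1 − d)p = 1/3 and (1 − d)(1 − p) = 1/2. The probability is 60 × (1/6) × (1/3)² × (1/2)³ × (1/3) = 4.6%. It illustrates the mechanism; the size of the effect is in Step 3.

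**Step 5: subjects still under observation.** The Period 2 DLT window is 56 or 70 days (Protocol 6.2.1.2.2), and starts are 96 hours apart (Protocol 5). Fifteen subjects could start within 14 × 4 = 56 days. A treated count would then also include, as non-DLTs, subjects whose follow-up has barely begun.

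**The case against.** The strongest reply is that 'treated' only fixes when looks begin, and that everything else points to evaluable subjects: the cohort of 15, a table that ends at the same 15, the restriction of DLT analysis to evaluable subjects, and tables that reproduce on that reading. This largely stands. A reader might infer that the rule does count treated subjects and that Table 11 overstates the protection. The documents do not support that: nothing says non-evaluable subjects stay in the denominator, and Table 11 is right for its own model. What survives is that nothing removes them either, and the only word attached to the count is 'treated'.

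The size can also be overstated. At a 20% share with monitoring ended at 15 treated, P(stop) falls to 28% and 51% at true rates of 30% and 40%. But the protocol replaces subjects to reach 15 evaluable, and its enrolment figures imply 16.7%. Even 20% is probably an upper figure for DLT-free loss. It includes adverse-event discontinuations, and treatment-related toxicity leading to removal from study is itself a DLT (Protocol 6.2.1.2.3).

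The Bayesian rule is not the only safeguard: the DLRT reviews adverse events in the DLT window and may terminate dosing (Protocol 6.2.1.2.1). That stands, but the review is discretionary and does not define the rule's denominator.

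Finally, relabelling alone is not enough, because Period 2 evaluability is itself unsettled. That is correct and is taken into the fix.

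**Conclusion.** The point holds as an undefined denominator in a safety stopping rule, present in both documents. Tables 10 and 11 are correct when every counted subject is DLT-evaluable.

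If the rule is applied literally to treated subjects, it can stop less often than Table 11 states. At true DLT rates of 30% and 40% the loss is about 3 to 4 points with 5% non-evaluable, 12 to 13 points at the 16.7% implied by the enrolment figures, and 15 to 17 points at 20%. These sizes rest on three assumptions: early leavers are DLT-free, they occur independently of toxicity, and the same posterior criterion is carried past 14 treated. The documents do not establish that the rule will be run this way, only that their wording permits it.

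**What to change.** 1. In Protocol 10.2 and SAP 3.1.3, replace 'fifth subject treated' with 'fifth DLT-evaluable subject' wherever it occurs.
2. Head Protocol Table 10 and SAP Table 1 'Cumulative number of DLT-evaluable subjects'.
3. State that replaced, non-evaluable subjects enter neither numerator nor denominator.
4. State how subjects still inside the DLT window are counted at each look. A DLT makes a subject evaluable at once, while others qualify only later, so the choice affects early looks.
5. Reconcile the Period 2 evaluability definition. Protocol 6.2.1.2.2 gives a Period 2 window but no Period 2 criterion, although the DLT analysis set refers there. Protocol 3.4.2 uses 85% of the first 8 doses (0.85 × 8 = 6.8, so 7 of 8). SAP section 6 uses 5 days at the target dose, or a separate cIV-based criterion when Cycle 2 is given. These passages must be made to agree.

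The cost is a short text change in both documents plus agreement on items 4 and 5. The boundaries and Table 11 can stay as they are, and no extra subjects are needed.
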